10.1. Data Management

10.2. Monitoring Arrangements

10.3. Data Management

11. Adverse Events and Termination

An AE is any adverse change from the participant's baseline condition, and is considered as any unfavorable and unintended sign or symptom or disease that occurs over the course of the clinical trial, whether related or unrelated to PAP therapy. All clinically significant AEs occurring during the clinical trial that were not present prior to the commencement of PAP therapy, will be recorded in the CRF, source document, and Adverse Event Log, and followed up by the PI until resolution or stabilization occurs in accordance with GCP. The collection of AE data will commence once the participant is consented into the trial and up to 24 hours after the Toffee Full face mask is returned following and the participant has completed the study. After this 24-hour period, AE information will no longer be collected.

Serious adverse events (SAE) are considered those which result in any of the following outcomes, regardless of their relationship to PAP therapy:

- Death
- Life-threatening AE
- Unplanned in-patient hospitalization or prolongation of existing hospitalization
- Persistent or significant disability or incapacity
- Congenital abnormality or birth defect

All SAEs will be recorded on a Serious Adverse Event Form, and any additional material or medical records will be de-identified by the PI or CI before it is affixed to the document.

Due to the nature of the delivery of PAP therapy, there are a number of expected side effects that may occur when using the Toffee full-face mask. These are disclosed in the PIS/ICF and will be documented in the CRF but not as adverse events. These are also documented below in Section 11.2.

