5.4. Enrolment eligibility

Inclusion criteria:

[figure not shown]
- Persons who are ≥ 22 years of age
- Persons who weigh ≥ 66 lbs (30 kgs)
- Persons who have been prescribed PAP (APAP, BPAP or CPAP) therapy by a physician
- Persons who are compliant with PAP therapy for ≥ 4 hours per night for 70% of nights for at least two weeks prior to enrolment in the trial
- Persons who are currently using a full face mask
- Persons who have an IPAP pressure of < 30 cmH₂O
- Persons who currently use a PAP therapy device with data recording capabilities
- Persons who are fluent in spoken and written English
- Persons who possess the capacity to provide informed consent

Exclusion criteria:

- Persons who are intolerant to PAP therapy
- Persons who are required to use PAP therapy for more than 12 hours per day or for extensive periods other than sleep or naps
- Persons using nasal or nasal pillows masks
- Persons who possess, or suffer from, anatomical or physiological conditions which make PAP therapy inappropriate
- Persons who are pregnant or think they may be pregnant
- Persons who use a PAP therapy machine for the delivery of medicines, except supplemental O₂
- Persons who currently have cold or flu like symptoms at the time of recruitment
- Persons who have tested positive for COVID-19 within the previous 28 days prior to enrolment

Participants can be current users of any full-face mask.

[REDACTED]

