5.5. Informed consent

Participants will be pre-screened for eligibility according to the inclusion and exclusion criteria and recruited by the three investigation sites from their database of patients by email or phone (using the RS, Appendix 15.1). If a patient is willing to participate in the clinical trial, informed consent will be obtained, individually or in groups, at the investigation site during Visit 1. A CI or the PI identified in the Delegation of Authority (DOA) will be present to witness the informed consent taking place and to answer any questions potential participants have relating to the clinical trial. Participants will be given the opportunity to read over the Informed Consent Form (ICF; Appendix 17.2), before being given an overview of clinical trial procedures and risks associated with partaking, by the CI or PI. All participants will be provided with a photocopy of the signed ICF before clinical trial procedures commence. No further physical or electronic copies of ICFs will be created. Each enrolled participant will be allocated a unique and random pre-generated 4-digit Subject Identification Number (SIN), which will be recorded in the Subject Identification Log (SIL). The SIL and all ICFs will be stored separate to all other clinical trial documentation at the investigation site to maintain anonymity of the feedback obtained from participants during the clinical trial. Details of the informed consent, such as the date and time it was obtained from participants, as well as the activities that were consented to, will also be recorded in the Case Report Form (CRF).

6. Investigational Product

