7.10. Participant Procedure

[figure not shown]
[REDACTED]

[REDACTED]

[Redacted]

[Redacted]	[Redacted]	[Redacted]
[Redacted]	[Redacted]	[Redacted]

Additionally, the PI may withdraw a participant at any time for the following reasons:

- Protocol violation
- Safety concerns
- Serious illness
- AE/SAE

The reason for participant discontinuation in the clinical trial is to be recorded in the CRF.

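### Section 11 defines AEs against the participant's baseline but limits recording by a date before the trial, and it withholds AE status from new or worsened expected mask effects that meet its definition

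*Combined protocol and SAP*

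**What the plan says.** The opening text of section 11 (Adverse Events and Termination) contains four statements that have to work together.

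- Definition: "An AE is any adverse change from the participant's baseline condition". It extends to any unfavorable, unintended sign, symptom or disease during the trial, whether or not PAP is the cause.
- Recording: "All clinically significant AEs occurring during the clinical trial that were not present prior to the commencement of PAP therapy, will be recorded". The entries go in the CRF, the source document and the Adverse Event Log, and the same sentence requires the events to be "followed up by the PI until resolution or stabilization occurs in accordance with GCP".
- Collection window: "The collection of AE data will commence once the participant is consented into the trial". Section 5.5 dates this step: "informed consent will be obtained, individually or in groups, at the investigation site during Visit 1".
- Expected side effects of the Toffee mask: "These are disclosed in the PIS/ICF and will be documented in the CRF but not as adverse events". The text then points to section 11.2, which is headed Foreseeable Adverse Events.

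Section 5.4 requires participants to be compliant with PAP "for at least two weeks prior to enrolment in the trial" and to be using a full face mask already. Section 11 requires every SAE to be put on a dedicated form, whatever its relation to PAP, and section 11.3 requires every SAE to be on the AE log.

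**The concern.** The definition and the recording rule look back to different times. The definition looks back to baseline and the recording rule to the start of PAP. For established PAP users these cannot be the same date. A site could therefore hold an event that is an AE by definition and yet, on the wording of the next sentence, need not be entered in the log or followed up. Section 5.5 mentions three investigation sites, and they could classify the same recurrence differently.

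The second problem does not depend on how the first is read. Section 11 gives a broad AE definition with no exception for expectedness, then withholds AE status from expected effects, and then refers to them under a heading that calls them adverse events.

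At stake is what the AE Log and the AE count mean in the final report. A reader who takes the count as the mask's full tolerability record would not be seeing the expected device effects.

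**Working it through.** The plan gives no figure on this point and no arithmetic applies. The check sets the rules side by side and runs each type of non-serious event through them. One assumption is needed: that baseline means the participant's condition on entering the trial. The visible text does not date it, but collection from consent points that way.

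Step 1, order of dates. Section 5.4 places at least two weeks of compliant PAP use before enrolment, and section 5.5 places consent at Visit 1. So the start of PAP comes before trial baseline and consent for every participant.

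Step 2, classification of clinically significant, non-serious events.

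| Event | AE by definition? | Recorded as an AE? |
|---|---|---|
| New after consent, not an expected effect | Yes | Yes |
| Present before PAP; recurs or worsens on the trial mask | Yes | Literal reading: not required. Other reading: yes, the worsening is the new AE |
| Arose between PAP start and consent, unchanged | No | No, because the recording rule covers only AEs |
| Arose between PAP start and consent, worsens, not an expected effect | Yes | Yes |
| Expected effect, same as at baseline | No | No |
| Expected effect, new or worse than baseline | Yes | No, CRF only, by the stated rule |

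Step 3, where the rules disagree. Two rows conflict. The second row conflicts on one of two available readings. An example is a symptom that was controlled on PAP at consent and returns when the trial mask leaks. The last row conflicts whichever of those readings is taken.

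Step 4, follow-up. The follow-up duty is part of the recording sentence and so attaches to recorded AEs. The visible text does not say whether it also covers expected effects.

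Step 5, what is protected. SAEs from any cause reach the AE log. Expected effects remain documented in the CRF. For a participant who stops, section 7.10 adds: "The reason for participant discontinuation in the clinical trial is to be recorded in the CRF".

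**The case against.** The best defence of the recording sentence is that it filters AEs, not conditions. An AE is by definition a change, and a worsening during the trial cannot have existed before PAP began. On that reading the clause excludes nothing. This stands as a possible reading, so the first problem is an ambiguity and not a certain loss. It also means the clause does no work and can be replaced without harm. The sponsor may instead have meant the start of trial-mask use, but the text does not say so.

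For expected effects, the defence is that separate handling is an explicit, disclosed rule, that participants already wear full face masks, and that the section 11.2 list and the CRF fields are not in the public text. Much of this stands. An effect unchanged from the usual mask is not an AE, so the point is limited to new or worse effects. The unseen text may set a severity limit or a follow-up rule, so its absence from the visible pages is not held against the plan. What remains is that the definition has no exception for expectedness and the exemption contradicts it.

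It is also true that no visible endpoint in section 7.4 and no visible analysis in section 9 uses an AE count. That bears on severity.

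A reader might infer three stronger points that the documents do not support.

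- That mask-related skin injury is missing from the AE count. Section 7.13 names such injuries from a general device database, but nothing visible says they are on the section 11.2 list.
- That participants who switch back to their usual mask disappear from both the AE count and the pass/fail analysis. This needs an expected effect, a switch, clear proof of other-mask use and exclusion under section 9.6, which requires the reason to be documented. That chain is speculative.
- That the recording rule lets in old problems from the usual mask. The AE definition already screens those out.

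**Conclusion.** The AE rule is wrong as written because it is internally inconsistent. The severity is minor.

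The reference points for defining and recording an AE differ for every participant. The consequence, a possible undercount of non-serious pre-PAP conditions that recur or worsen, arises on the literal reading only. The omission of new or worsened expected effects from the AE Log and AE count follows from the stated rule.

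No size can be given: the documents contain no event rates, and the list of expected effects is not visible. No specific injury is claimed to be affected. The conclusion rests on baseline meaning the condition at trial entry, and on the unseen part of section 11 not redefining an AE.

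**What to change.** Replace the recording filter with wording such as: *clinically significant AEs that were not present at consent, or that recurred or worsened after consent*. Definition, recording and collection then share one reference point.

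Keep expected effects in the CRF, mark those that are new or worse than baseline with an expected flag, and tabulate them beside the other AEs in the final report.

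Reconcile the statement that expected effects are not AEs with the heading of section 11.2 and with the follow-up sentence. The sponsor should state whether the follow-up duty covers these effects; no position is taken here on what that duty should be.

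The cost is two or three sentences in section 11 and, if not already present, one flag on an existing CRF entry. The downside is slightly more data entry and a higher reported event count, some of it background fluctuation unrelated to the mask.

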11.2. Foreseeable Adverse Events

11.3. Reporting Adverse Events

Any SAEs, due to any cause, that occur during the clinical trial period, must be reported immediately, or within the next business day, by telephone to the sponsor. In addition to the initial telephone report, a SAEF must be completed and sent via email to the sponsor. All SAEs must also be recorded on the AE log. Additionally, all SAE's must be reported to HDEC as per HDECs reporting requirements.

11.4. Early Termination

The clinical trial may be discontinued at any time on the advice of the responsible investigator or on the basis of new information regarding safety or efficacy arising. Additionally, the clinical trial may be terminated if progress is unsatisfactory. The following documentation is required if the appropriate party terminates a clinical trial.

- PI: If the PI terminates or suspends a clinical trial without prior agreement of the sponsor, the PI should inform the institution, where required by the applicable regulatory requirements and the PI/institution should promptly inform the sponsor and HDEC, and should provide the sponsor and HDEC a detailed written explanation of the termination or suspension.
- Sponsor: If the sponsor terminates or suspends a clinical trial, the PI should promptly inform the institution, when and where required by the applicable regulatory requirements, and the PI/institution should promptly inform HDEC and provide a detailed written explanation of the termination or suspension.
- HDEC: If HDEC terminates or suspends its approval/favorable opinion of a clinical trial, the PI should inform the institution, when and where required by the applicable regulatory requirements. The PI/institution should promptly notify the sponsor and provide the sponsor with a detailed written explanation of the termination or suspension.

12. Publication Policy

[figure not shown]

13. Approval

14. References

[figure not shown]
1. Senaratna, C. V. *et al.* Prevalence of obstructive sleep apnea in the general population: A systematic review. *Sleep Medicine Reviews* (2017). doi:10.1016/j.smrv.2016.07.002
2. Balachandran, J. S., Masa, J. F. & Mokhlesi, B. Obesity hypoventilation syndrome: Epidemiology and diagnosis. *Sleep Medicine Clinics* (2014). doi:10.1016/j.jsmc.2014.05.007
3. Aurora, R. N. *et al.* Practice parameters for the surgical modifications of the upper airway for obstructive sleep apnea in adults. *Sleep* (2010). doi:10.1093/sleep/33.10.1408
4. Sullivan, C. E., Berthon-Jones, M., Issa, F. G. & Eves, L. Reversal of Obstructive Sleep Apnoea by Continuous Positive Airway Pressure applied through the nares. *Lancet* (1981). doi:10.1016/S0140-6736(81)92140-1
